The aim of this study is to explore the role of the CDED combined with PEN in both inducing and maintaining remission of CD in adults, taking into consideration important objective biomarkers such as faecal calprotectin (FC) (21) along with patient reported outcomes. More precisely, our primary goal is to investigate whether CDED with PEN could lead to a significant decrease in feacal calprotectin concentration. In view of the existing dietary guidelines for adult Crohn's disease patients (7,8) and considering that dairy constitute the main dietary source of calcium, researchers wish to challenge patients in remission with a gradually increasing exposure to dairy products, to assess tolerability, prospecting for the development of a personalized remission maintenance diet based on the CDED principles. Our aim is to examine the proportion of patients with significant feacal inflammation elevation following the dairy introduction.

We intent to investigate the effectiveness and feasibility of this dietary strategy in terms of changes in clinical and biochemical indices, patient's quality of life and nutritional status as well as patients' adherence and acceptance of the diet. Finally, we plan to re-evaluate patients' dietary habits and clinical outcomes, 6 months after the beginning of the study to address the established dietary adaptations, as well as the sustainability and durability of potential benefits of the dietary intervention.

Design and Methods

The proposed project is a randomized controlled clinical trial which is held in Evangelismos General Hospital of Athensin collaboration with the Department of Food Science & Human Nutrition of Agricultural University of Athens. Briefly, eligible patients are adults with established Crohn's disease with ileal and/or colonic involvement who receive their IBD care at the hospital's Gastroenterology Unit (see eligibility criteria below). Patients with active mild-to-moderate disease, defined by aHarvey–Bradshaw Index (HBI) score of 5–14 points, or inactive disease (HBI<5) are eligible for enrolment. Detailed information about the purpose and the study procedures will be given to all patients and consent form will be signed. The study protocol has been approved by the Ethics committee of the hospital.

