Patients will be randomly assigned 1:1 to either CDED plus PEN plus dairy products or PEN plus usual nutritional care. In detail, half of the patients in remission will follow the first stage diet (CDED+PEN) for 4 weeks and will continue with CDED + PEN + dairy products for another 4 weeks. The other half will be given PEN plus the usual advice for a healthy dietary pattern. PEN will cover the 50% of total energy requirements for the first 4 weeks and the 25% during the second 4 weeks. Half of the patients with active disease will follow the first stage diet (CDED + PEN 50%) for 6 weeks and then, the responders will continue with adding the dairy product while PEN will cover 25% of the total energy requirements, for 4 more weeks. The other half will be given PEN plus the usual advice for a low residue diet. Low lactose, low fat and low additive dairy foods will be given, namely Greek yogurt 2% fat and light yellow cheese with 10-12% fat, in calculated portions to meet tailored energy, protein and calcium requirements. After the end of the intervention period, patients will be advised to reintroduce foods that were eliminated and to follow a maintenance diet. All participants will attend study visits at the beginning, in the middle (week 8 or week 10, for patients entering the study in remission or with active symptoms, respectively) and at the end of the study, at which points questionnaires will be completed, anthropometric measurements will be conducted and biological samples will be collected. The last follow-up will take place in week 24. In the meanwhile, phone calls by a researcher dietitian will be held to assess adherence and support the patients.24-hour diet recallsand the modified Medication Adherence Report Scale (MARS) questionnaire (16) will be used to address compliance along with the physician's assessment.

At length, our methodological approach includes:

i) Anthropometry

- (1) Weight (kg) measurement, [Time Frame: Baseline, week 4, week 8 (Baseline, week 6, week 10 for patients entering the study with active disease), week 24]
- (2) Height (m) measurement, [Time Frame: Baseline],
- (3) Body mass index (BMI) (kg/m²) calculation
- (4) Waist, neck and midarm circumferences (cm), triceps skinfold (mm) measurement [Time Frame: Baseline, week 8/w10]
- (5) Body composition analysis (Fat mass, fat %, fat free mass, phase angle)
 by Bioelectrical Impedance Analysis (BIA) [Time Frame: Baseline, week
 8/10]

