- Any proven current infection such as positive stool cultures or positive tests for parasites or C. difficile.

The proposed project has a duration of thirty-six (36) months. The 1st phase that has already been completed included preparation and printing of questionnaires, creation of recipes based on the principles of the dietary intervention. The recruitment process is anticipated to start in September 2022 and to be completed by March 2024.

Statistical Analysis Plan (SAP)

Based on pilot data (18) we performed a sample size calculation using the GPower 3.0.10 software (http://www.softpedia.com/get/Science-CAD/G-Power.shtml). A sample of 140 individuals is sufficient to achieve statistical power > 80 %, at a significance level of a = 0,05 for two-sided statistical tests. All continuous variables will be assessed for normality with the Kolmogorov–Smirnov test (cutoff p < 0.01), to use parametric or non-parametric tests, as appropriate. Chi-squared or Fischer's test will be used to analyze categorical variables. Continuous variables will be analyzed by using Mann Whitney U test and t-test for paired-samples or the Wilcoxon signed rank). For paired measures (e.g. FC concentration) before and after the intervention, we will calculate the percentage change for each patient relative to baseline. Logistic regression models will be used to explore how age, sex, phenotypic factors (disease location and activity), MD-scoreat baseline, adherence and intervention grouping would contribute to significant HBI or FC concentration drop.

Bibliography:

3;396(10256):e56]. *Lancet*. 2017;390(10114):2769-2778. doi:10.1016/S0140-6736(17)32448-0

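### The between-arm comparison of faecal calprotectin adjusts for neither baseline value nor entry stratum, which costs power; percentage change should be descriptive only

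*Combined protocol and SAP*

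**What the plan says.** The protocol (Objectives) states that "our primary goal is to investigate whether CDED with PEN could lead to a significant decrease in feacal calprotectin concentration". No time point, scale or effect measure is attached to this goal.

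Design and Methods enrols two kinds of patient: active disease with HBI 5 to 14, "or inactive disease (HBI<5) are eligible for enrolment". Allocation is 1:1 and is described as a halving within each group: "half of the patients in remission will follow the first stage diet (CDED+PEN) for 4 weeks", with a parallel statement for active entrants. The two groups differ by design:

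| | Remission entrants | Active entrants |
|---|---|---|
| First-stage diet | 4 weeks | 6 weeks |
| FC sampling after baseline | weeks 4 and 8 | weeks 6 and 10 |
| Control-arm advice | healthy dietary pattern | low residue diet |

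The SAP gives one instruction that mentions FC as a continuous measure: "we will calculate the percentage change for each patient relative to baseline". Its tests are given in one sentence: "Continuous variables will be analyzed by using Mann Whitney U test and t-test for paired-samples or the Wilcoxon signed rank". The choice between parametric and non-parametric tests follows a normality check: "All continuous variables will be assessed for normality with the Kolmogorov–Smirnov test (cutoff p < 0.01". The only model with covariates is a logistic regression exploring "how age, sex, phenotypic factors (disease location and activity), MD-scoreat baseline, adherence and intervention grouping would contribute to significant HBI or FC concentration drop". Disease activity is in that list; baseline FC is not.

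**The concern.** Baseline FC and HBI are collected on every patient, and entry stratum determines diet length, sampling week and control advice. A two-sample rank test on change scores uses none of this. FC varies considerably within and between patients, so a comparison that ignores the baseline as a covariate carries avoidable noise. In a trial with a single N of 140 across both strata, that lowers the chance of detecting a real effect on the primary biomarker.

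The scale is a second, smaller issue. Percentage change stops at -100% below and has no upper limit: a halving scores -50%, and the doubling that reverses it scores +100%. If the SAP's percentage changes are reported as arithmetic means, a real fall may look like no change or a rise.

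**Working it through.** **The plan's own figure.** The SAP states N = 140 for power above 80% at two-sided 0.05, but gives no effect size, SD, rate, endpoint or test. The figure can be neither reproduced nor refuted. At 70 per arm it is consistent with a standardised difference of about 0.475 (power 80.2%) or with response rates of 50% and 73% (power 80.5%), among others.

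**Inputs.** From the documents: 1:1 allocation, so 70 per arm; two-sided alpha 0.05; two strata. Assumed, because the documents give no FC data: log-normal FC, half the patients in each stratum, true log effect 0.4 (exp(-0.4) = 0.67, a 33% fall), between-patient log SD b = 0.6 to 1.0, within-patient log SD w = 0.4, 0.6 or 0.8.

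**Step 1: power by formula.**
- The log change has variance 2w². ANCOVA on baseline has residual variance (b² + w²)(1 - r²), where r = b²/(b² + w²).
- The standard error of the arm difference is the square root of 2 × variance / 70. Power is approximately Φ(0.4/SE - 1.96).
- For b = w = 0.6, log change: variance 0.72, SE 0.143, power Φ(0.83) = 80%.
- For b = w = 0.6, ANCOVA: r = 0.5, residual variance 0.72 × 0.75 = 0.54, SE 0.124, power Φ(1.26) = 90%.
- The variance ratio is 0.75, so an unadjusted log-change analysis would need about 140/0.75 = 187 patients to match ANCOVA on 140.

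**Step 2: power by simulation.** This compares the test the SAP names with the adjusted analysis.

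| Within-patient log SD | Mann-Whitney on % change | Log ANCOVA, baseline and stratum |
|---|---|---|
| 0.4 | about 98% | about 100% |
| 0.6 | about 78% | 85-89% |
| 0.8 | 52-55% | 63-73% |

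Ranges cover b = 0.6 to 1.0; the lower ANCOVA figures belong to b = 1.0. Simulated type I error is near 5% for every method.

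**Step 3: where the loss arises.** In one run at b = w = 0.6, power was 77% for Mann-Whitney on % change, 78% for a t-test on log change, 86% for log ANCOVA with baseline only, and 89% with stratum added. Changing the scale alone gains 1 to 3 points; nearly all the gain comes from adjustment.

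**Step 4: arithmetic mean of percentage change.** The log change has variance 2w², so with true log change -δ the mean is 100 × (exp(w² - δ) - 1).
- No true change (δ = 0): exp(0.16) - 1 = +17%, exp(0.36) - 1 = +43%, exp(0.64) - 1 = +90%. The median is 0 each time.
- A true 33% fall (δ = 0.4): exp(-0.04) - 1 = -4% at w = 0.6, and exp(0.24) - 1 = +27% at w = 0.8. The median is -33% in both cases.

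**The case against.** The strongest reply is that percentage change does little harm under the test actually named. Percentage change is a monotone function of the log ratio, so Mann-Whitney gives the same result on either. The SAP lists no unpaired t-test. Its wording leaves one possible, but the Kolmogorov-Smirnov rule rejected normality of percentage change in 92-100% of simulated trials under most settings, and in roughly half at w = 0.4, where power is ample anyway. This stands: the upward pull concerns a mean that the SAP does not say it will report. A reader might infer that the FC test is biased or its error rate inflated; the documents and the calculations do not support that.

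A reader might also infer that remission entrants are worst affected because their FC is low. Under the log-normal model, exp(w²) - 1 does not depend on FC level, so the effect is equal in both strata. It becomes larger at low FC only with further assumptions: with additive error SD 30 µg/g and a floor of 10 µg/g, one simulation gave +108% in remission against +84% in active entrants. The documents contain nothing to establish this. Nor does a move from 30 to 60 µg/g scoring the same as one from 400 to 800 argue against percentage change in favour of logs, since both score log 2.

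Two further points stand. Disease activity does enter the exploratory logistic model, so it would be wrong to say the plan never uses the stratum. And the SAP says percentage change will be calculated, not that it is the sole or primary test variable.

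What the reply does not answer is that no named between-arm analysis of FC uses baseline FC, and none of FC as a continuous measure uses stratum. The paired tests compare times within patients, not arms. The logistic model dichotomises FC at a threshold that is not defined.

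**Conclusion.** The concern holds as a loss of efficiency in the comparison that matters most. The cost is 1 to 2 power points at within-patient log SD 0.4, about 7 to 11 at 0.6 and about 11 to 18 at 0.8. Its size therefore depends on FC variability, which the documents do not give, and could be small. All figures assume log-normal FC, equal strata and a common proportional effect.

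The distortion of mean percentage change is real, but conditional on means being reported. It is a matter of presentation, present in both arms.

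This does not show that 140 patients are too few, because the basis of that number is not given. The change is worth making because it uses data already being collected.

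**What to change.** In the SAP, name the between-arm FC analysis as an ANCOVA of follow-up log FC on arm, baseline log FC and entry stratum (HBI below 5, or 5 to 14). State one time point per stratum: week 4 (remission) and 6 (active), or week 8 and 10. The choice should match the goal, since the earlier pair falls at the end of the diet stage without dairy and the later pair after dairy has been added. Report the adjusted geometric mean ratio with 95% CI, overall and by stratum. Keep per-patient percentage change as a description only, by median and IQR.

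The cost is a few lines of SAP text and slightly more analysis work, with no new data, visits or patients. The one drawback is that results appear as ratios. A ratio of 0.67 can be stated in the text as a 33% lower FC.

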- (6) Handgrip strength (kg) assessment by dynamometer [Time Frame: Baseline, week 8/w10]
- Dietary habits assessment, using a semi-quantitative food frequency questionnaire (FFQ), to assess dietary habits and adherence to the Mediterranean diet (MD-score) [Time Frame: Baseline, week 24] and 24-

recalls [Time Frame: Baseline, week 2/w3, week 4/w6, week 6/w8, week 8/w10]

- iii) Physical activity assessment, using HPAQ questionnaire [Time Frame: Baseline, week 8/w10]
- iv) Health-related quality of lifeassessment, defined by the selfadministered 32-item Inflammatory Bowel Disease questionnaire (IBDQ) score. Higher IBDQ scores indicate better outcomes. Clinical response defined as increase ≥16 points [Time Frame: Baseline, week 8/w10]
- v) Medical history (e.g.,prior GI surgery, comorbidities) data collection and disease activity assessment by the HBI. Clinical response is defined as baseline HBI score decrease of ≥ 3[Time Frame: Baseline, week 4/w6, week 8/w10]
- vi) **Blood and Feacal samples collection** by specializes staff [Time Frame: Baseline, week 4/w6, week 8/w10]
 - (1) **Blood samples analysis** by the hospital's lab to estimate serum **CRP** and **albumin**
 - (2) Feacal samples analysis by certified labs to estimate Feacal calprotectin concentration (μ g/g)
- vii) Nutrition education according to the intervention principals and prescription of nutritional supplements (liquid formulas-PEN) [Time Frame: Baseline]. Support line for patients' support will be available.
- viii)**Handle-analysis** of the questionnaires and **data entry** in electronic databases [Microsoft® Excel, IBM SPSS Statistics®, Nutritionist Pro®]
- ix) Statistical analysis/interpretation of results.

Eligibility Criteria:

Inclusion Criteria:

- Participants must have an established diagnosis of CD
- Individuals able to give informed consent and willingness to participate Exclusion Criteria:
 - Age < 18 years old
 - Previous extensive bowel resection
 - Reported pregnancy or lactation
 - Current stoma or abscess
 - Clinically significant stricture
 - Introduction of or change in dose of drug therapy within the past 8 weeks

- Comorbidities including diabetes or coeliac disease, or other concomitant serious comorbidity e.g. significant psychiatric, hepatic, renal, endocrine, respiratory, neurological, cardiovascular, neoplastic or other autoimmune disease
- Food allergies or intolerances, which do not permit participation in the study

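### The SAP's only regression models set adherence, assessed after randomisation, beside intervention grouping, so their intervention odds ratio is not the effect of assignment

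*Combined protocol and SAP*

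**What the plan says.** The Statistical Analysis Plan (SAP) section names one kind of regression. Logistic models will explore how age, sex, disease location and activity, "MD-scoreat baseline, adherence and intervention grouping would contribute to significant HBI or FC concentration drop". Every other test listed there is an unadjusted two-group or paired test.

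Three places in the protocol show what adherence is.

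- **When and how it is assessed.** Under Design and Methods, between study visits, "phone calls by a researcher dietitian will be held to assess adherence and support the patients". Diet recalls and the modified MARS "questionnaire (16) will be used to address compliance along with the physician's assessment". The recall schedule runs "recalls [Time Frame: Baseline, week 2/w3, week 4/w6, week 6/w8, week 8/w10", so four of its five time points fall after assignment.
- **It is a result of the study.** Under Objectives, the strategy is to be judged partly on patients' "adherence and acceptance of the diet".
- **It refers to different regimens.** Patients are assigned to "either CDED plus PEN plus dairy products or PEN plus usual nutritional care". PEN is common to both arms; the rest of the diet is not.

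Adherence to the Mediterranean diet at baseline is a separate covariate (the MD-score), so the adherence term cannot mean that.

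**The concern.** Randomisation protects a comparison of the arms that is unadjusted or adjusted for variables fixed before assignment. It does not protect a comparison within levels of something that happens afterwards. Adding adherence to the model can change the intervention coefficient in two ways:

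- If assignment affects adherence and adherence affects response, the coefficient drops the part of the effect carried through adherence. It then answers a different question.
- If assignment affects adherence and some unmeasured factor (motivation or symptom burden, say) drives both adherence and response, then adherers in the two arms are no longer alike. The coefficient is biased even when the diet does nothing.

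Two features of this trial add to the difficulty. One adherence coefficient pools different behaviour in the two arms. In addition, recalls coincide with HBI and FC assessments at weeks 4/6 and 8/10, and among CDED patients with active disease only responders go on to the dairy stage. An adherence measure spanning both stages could therefore partly reflect response; the SAP does not define it.

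The SAP names no primary between-arm analysis, estimand or analysis population. The adherence-adjusted odds ratio is the only adjusted between-arm estimate it describes, so it could be reported as the adjusted effect of CDED.

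**Working it through.** **The plan's own figure.** The SAP gives 140 patients for more than 80% power but no effect size, so that figure cannot be reproduced. This point needs it only for arm size: 140 randomised 1:1 gives 70 per arm.

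**Model used for illustration.** Every input except 70 per arm is an assumption. Let U be an unmeasured standard normal factor and A indicate adherence:

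- logit P(A = 1) = a_arm + s·U
- logit P(response) = b0 + bT·arm + bA·A + s·U

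Averaging over U by 80-node Gauss-Hermite quadrature gives the large-sample response rates. Logistic models for response are then fitted on arm alone, and on arm plus A.

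**No true effect** (bT = bA = 0, 40% response in both arms). Take s = 1.0 with adherence 80% in control and 60% in CDED:

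| | Control | CDED | Odds ratio |
|---|---|---|---|
| Non-adherent | 26.7% | 30.1% | (0.301/0.699)/(0.267/0.733) = 1.18 |
| Adherent | 43.3% | 46.6% | (0.466/0.534)/(0.433/0.567) = 1.14 |
| Whole arm | 0.2×26.7 + 0.8×43.3 = 40.0% | 0.4×30.1 + 0.6×46.6 = 40.0% | 1.00 |

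The arms are identical overall, yet CDED looks better in both strata because they hold different kinds of patients. The pooled adherence-adjusted odds ratio is 1.152. Over the range of s:

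| Adherence, control / CDED | s = 0.5 | s = 1.0 | s = 1.5 |
|---|---|---|---|
| 80% / 60% | 1.046 | 1.152 | 1.277 |
| 60% / 80% | 0.956 | 0.868 | 0.783 |
| 80% / 80% | 1.000 | 1.000 | 1.000 |

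The unadjusted odds ratio is 1.000 throughout. Smaller gaps matter less: with 80% in control, the adjusted value is 1.02-1.13 at 70% in CDED and 1.01-1.06 at 75%.

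**Against the precision of the trial.** Expected responders and non-responders per arm are 70×0.4 = 28 and 70×0.6 = 42. The unadjusted standard error of the log odds ratio is √[2(1/28 + 1/42)] = 0.345; with adherence in the model it reaches 0.366. The largest shift is ln(1.277)/0.366 = 0.244/0.366 = 0.67 standard errors.

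**Error rate of the arm term.** In 20,000 simulated trials per scenario (two-sided Wald test at 0.05, 80%/60% adherence), the rejection rate with adherence in the model was 5.1%, 6.6% and 10.0% for s = 0.5, 1.0 and 1.5. Without it the rate was 4.7%, 4.8% and 5.1%. Reversing the adherence rates gave the same adjusted figures. Under 1% of replicates could not be fitted and were left out. A normal approximation agrees: a shift of 0.67 standard errors gives P(Z > 1.29) + P(Z < −2.63) ≈ 0.099 + 0.004 = 10.3%.

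**An assumed real effect** (bT = bA = 0.5, s = 1.0, control response 35%):

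| Adherence, control / CDED | Unadjusted OR | With adherence |
|---|---|---|
| 80% / 60% | 1.39 | 1.76 |
| 60% / 80% | 1.62 | 1.33 |
| 80% / 80% | 1.50 | 1.53 |

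Part of each gap is a change of estimand and not bias.

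**Different assumptions, same pattern.** A separate simulation with no true effect moved the odds ratio from 1.00 to 1.19 (adherence 67% control, 43% CDED) and from 1.00 to 0.88 (67%, 85%). With an effect acting only through adherence to CDED plus a common cause, it moved from 1.63 to 2.39. With adherence unrelated to response it stayed at 2.73.

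**The case against.** The strongest reply is that these models do not claim to estimate a treatment effect. The SAP uses them to explore which factors contribute to a drop, and adherence is a fair factor in a prognostic question. The chi-squared/Fisher and Mann-Whitney tests remain, and a randomised trial does not need covariate adjustment for an unbiased comparison. That stands, and it limits the weight of the point. But an exploratory label does not turn the coefficient into an effect of assignment, and intervention grouping is itself one of the listed factors.

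Joint entry is also inferred: the SAP speaks of models in the plural and does not say that all covariates enter together. That is correct. One list of contributors to one outcome is still most naturally read as multivariable, and a sentence in the SAP would settle it.

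The magnitudes rest on assumptions, including a 20-point adherence gap; the 10.0% error rate is the worst case shown. The fitted models omit the SAP's baseline covariates, which might absorb part of a common cause. Applying one 40% response rate to all 140 may not suit HBI either: patients with HBI below 5 may enrol, Design and Methods defines response as a fall of at least 3, and those scoring 0-2 cannot achieve it. All of this stands. The figures show that the distortion is possible and how it behaves; they do not predict its size here.

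**Conclusion.** The concern holds. If the models are fitted as the SAP is most naturally read, the odds ratio for intervention grouping will not estimate the effect of assignment and is liable to bias in either direction. That conclusion rests on the documents alone: adherence is assessed after randomisation, relates to regimens that differ by arm, is a stated study result, and shares the model with intervention grouping.

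Size and direction cannot be derived, because the documents give neither adherence rates nor a definition of the covariate. Bias is near zero if adherence is equal in both arms and driven by the same factors. Under the assumptions shown, the shift is modest beside sampling error, though enough in the worst case to double the error rate of the arm term. The point deserves correction because the remedy is nearly free, but it does not undermine the unadjusted between-arm comparisons.

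**What to change.** In the SAP's logistic regression sentence:

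1. Estimate the adjusted intervention effect from a model containing intervention grouping and only pre-randomisation covariates: age, sex, disease location, disease activity at entry and baseline MD-score. State that these enter together, and that activity means the value before randomisation; the SAP gives it no time point.
2. Leave adherence out of that model and report it by arm as an outcome, with its definition.
3. Examine the association of adherence with response in a separate exploratory analysis within each arm, labelled non-causal. If a pooled model with adherence is kept for prognostic interest, state that its intervention coefficient is not a treatment effect.

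The cost is one or two sentences. No new data are needed, and no visit, measurement or part of the intervention changes.

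### The only adjusted analyses need a yes/no calprotectin drop, but the SAP fixes neither its cut-off nor its visit; a baseline-adjusted linear model of log calprotectin would use the data better

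*Combined protocol and SAP*

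**What the plan says.** The section on objectives makes a fall in FC the primary goal, without saying how large a fall counts as significant. Design and Methods, item vi, collects FC as a concentration at baseline, week 4 (week 6 for active entrants) and week 8 (week 10).

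The SAP handles FC in two ways:

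- **Unadjusted, continuous.** Each patient's percentage change from baseline is calculated. Continuous variables go to a Mann-Whitney test or to paired t or Wilcoxon signed-rank tests.
- **Adjusted, binary.** "Logistic regression models will be used to explore how age, sex, phenotypic factors (disease location and activity"), baseline Mediterranean-diet score, adherence and "intervention grouping would contribute to significant HBI or FC concentration drop".

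No other multivariable analysis is planned. HBI has a response definition in Design and Methods, item v: "Clinical response is defined as baseline HBI score decrease of ≥ 3". IBDQ has one too, an increase of at least 16 points. FC has none, either as a concentration or as a percentage. The SAP does not say that the HBI drop in the logistic model is the item v definition, and it names no visit for either drop.

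**The concern.** A logistic model cannot be fitted to FC until someone chooses the fall that counts and the visit at which it is judged. If that is done with the results in view, the nominal 5% level no longer holds. The visits are not interchangeable either, because dairy is added only after the first diet stage.

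The second cost is precision. FC is measured as a number, and cutting it in two discards information. Adjustment matters in this trial because it enrols patients in remission and patients with active disease, on different schedules. Yet the only model that accounts for activity and location is the one that discards information, and it does not list baseline FC as a covariate.

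**Working it through.** **1. The plan's own figure.** The SAP says "A sample of 140 individuals is sufficient to achieve statistical power > 80" per cent, "at a significance level of a = 0,05 for two-sided statistical tests". It cites pilot data but gives no effect size, SD, response rates, endpoint, test or dropout, so 140 can be neither reproduced nor refuted. Working backwards with 70 per arm (1:1 allocation), the standardised difference with 80% power is (1.960 + 0.842) × √(2/70) = 0.474 by the normal formula, or 0.477 for a t-test. I use 0.477 only as a benchmark; the documents do not state it.

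**2. Information lost by one cut.** Assume the change in log FC is normal, and let p be the share classed as responders. The efficiency of the binary analysis relative to the continuous one is φ(z_p)² / [p(1 − p)].

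| Split | Efficiency | Loss | 140 patients are worth |
|---|---|---|---|
| 50/50 | 0.3989² / 0.25 = 0.637 | 36% | 89 |
| 40/60 | 0.3863² / 0.24 = 0.622 | 38% | 87 |
| 30/70 | 0.3477² / 0.21 = 0.576 | 42% | 81 |
| 20/80 | 0.2800² / 0.16 = 0.490 | 51% | 69 |

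A third is therefore close to the minimum loss.

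**3. Power after a cut.** Assume an SD of 1.0 for log FC change, a control-arm mean change m, and an intervention mean lower by 0.477. For a fall of fraction f, the response rates are Φ(log(1 − f) − m) in control and Φ(log(1 − f) − m + 0.477) in intervention. For m = −0.3 and f = 50%, these are Φ(−0.393) = 0.347 and Φ(0.084) = 0.533. Simulated power of the unadjusted two-proportion test, 70 per arm, 40,000 trials per row:

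| Control mean m | 25% fall | 50% fall | 70% fall | 80% fall |
|---|---|---|---|---|
| 0 | 61.6% | 58.3% | 46.7% | 34.4% |
| −0.3 | 59.4% | 60.7% | 54.4% | 43.6% |
| −0.75 | 53.5% | 58.8% | 60.1% | 55.6% |

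The range is roughly 35–62%, against 80% for the uncut outcome. It depends on the cut-off and on m, neither of which the documents give.

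**4. Choosing the cut-off afterwards.** With no treatment effect, each single cut rejects in about 5% of trials. Taking the best of the four rejects in 14.8%, 15.0% and 14.5% for m = 0, −0.3 and −0.75. A separate run on normal data, with cut-offs defined by responder share, gave 5.1% for one cut, 8.8% for two, 10.2% for three and 15.2% for five. An open choice of visit would add to this.

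**5. Does a linear model do better?** Only if it includes baseline FC. Assume equal variances at both visits and correlation r between baseline and follow-up log FC. The benchmark effect is then 0.477 × √(2(1 − r)) in units of the follow-up SD. Adding baseline log FC divides this by √(1 − r²), which gives 0.477 × √(2/(1 + r)). Power at 70 per arm (t-test):

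| r | Follow-up log FC alone | With baseline log FC |
|---|---|---|
| 0.5 | 80% | 90% |
| 0.7 | 58% | 86% |
| 0.8 | 43% | 84% |

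At r = 0.7, for example, the standardised effects are 0.477 × √0.6 = 0.369 and 0.477 × √(2/1.7) = 0.517. Without its baseline, follow-up FC can do as badly as the dichotomised version.

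**The case against.** The SAP presents the logistic models as exploring predictors of response, not as the trial's treatment comparison, and FC is also compared on its continuous scale. That stands. The loss falls on the adjusted analyses only, and the point is not a fatal one. But these are the only models that adjust the arm comparison for anything, and an undefined outcome for the primary measure leaves the same gap in an exploratory model.

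HBI is largely settled. It has a 3-point definition that the SAP need only cite. The percentages above do not carry over to it: HBI is a discrete score with a floor, and patients entering at 0–2 cannot fall by 3.

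Two stronger readings are tempting:

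- **That the trial falls short of its stated power.** The SAP's "sufficient to achieve statistical power > 80" per cent is tied to no endpoint or test, so the 35–62% cannot be set against it. It is relative to an assumed continuous analysis with 80% power.
- **That the adjusted odds ratio is badly inflated by small-sample bias.** A true odds ratio of 2.5 is estimated at about 2.8–3.1 with 50–70 patients, 7 coefficients and a 50% event rate. That presumes a model in active entrants alone, which the SAP does not specify; activity is a covariate there. With all 140 patients and 8 coefficients the estimate is about 2.6–2.7. The documents give neither the mix of active and remission patients nor the event rates.

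**Conclusion.** The point holds for FC and for the adjusted analyses. The outcome of the logistic FC model is not defined, and choosing among four cut-offs after seeing the data would about triple the type I error, from 5% to about 15%. The documents do not show that anyone intends to do so; they leave it possible. Dichotomising costs at least about a third of the information on FC, and about half if responders are as few as 20%.

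The information and power figures assume normal log FC change; the power figures also assume 70 evaluable patients per arm and the 0.477 benchmark, and come from unadjusted tests, so they approximate the planned models. None of this undermines the unadjusted continuous comparisons. It is a cheap improvement.

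**What to change.** 1. Make the adjusted treatment comparison a linear model (ANCOVA) of log FC at one named visit, for example week 8 (week 10 for active entrants). Include arm, baseline log FC, disease activity at entry and the other baseline covariates already listed: age, sex, disease location and Mediterranean-diet score.
2. Fit the analogous model for HBI, with baseline HBI as a covariate.
3. Leave adherence out of these models. It is measured after randomisation and may be affected by the assigned diet, so the arm term would no longer be a clean randomised comparison.
4. Keep the logistic responder models as secondary. Fix one FC cut-off and one visit in the SAP before any follow-up FC is seen, and state that the HBI drop is the item v definition, a decrease of at least 3.
5. If a logistic model is fitted in a small subgroup, such as active entrants only, use Firth's penalty or fewer covariates.

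The cost is SAP wording and a little analysis work. No new data are needed, since baseline FC and HBI are already collected. The one drawback is that the main adjusted FC result is read as a ratio between arms rather than a responder rate, which the secondary models still supply.
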